3.3 Secondary Study Endpoints

Investigate measurable changes of patient characteristics and tissue and serum from fasting/CR conditions to determine a metric for evaluating this treatment in future studies.

- Weight: Weight will be monitored as a percent change and by body mass index as weight in kg divided by height in meters squared, at baseline, week 1, 3, 5 and 7, conclusion and 4 weeks after diet is complete.
- Body Fat Measurement: Body fat percentage will be done at baseline, conclusion and 4 weeks after diet is complete and will be determined by the Durnin-Womersley 4-fold technique. All skinfold measurements should be made on the right side of the body in mm using a body fat caliper. Body fat caliper will be placed 1 cm away from thumb and finger, perpendicular to the skinfold, and halfway between the crest and base of fold. A pinch will be maintained with the body fat caliper for 1 to 2 seconds before reading the caliper. Duplicate measurements will be taken at each site, allowing time for skin to regain normal texture and thickness. Measurements will be taken at the:
 - Biceps: Measured on a vertical fold at the upper arms frontside, half way between shoulder and elbow.
 - Triceps: Measured on a vertical fold at mid of the upper arms backside.
 - Scapula: Measured on a diagonal fold on the back, at the lower edge of the scapula. Angle of inclination should be 45°, clockwise.
 - Hip: Measured on a diagonal fold straight over the pelvis, close to the navel. Angle of inclination should be 30°, clockwise.
- Bioimpedance: Bioimpedance will be taken at baseline, conclusion and 4 weeks after diet is completed and will be measured in Ω/m^2 .
- Vitals: Vital signs including temperature, blood pressure, heart rate and respiratory rate will be monitored weekly.
- Serum (collection procedures detailed in Appendix VI):
 - At initiation of diet, conclusion of diet and 4 weeks after diet is complete, fasting labs will be drawn:
 - Clinical Lab: CBC, basic metabolic panel, hemoglobin A1C, triglycerides, insulin, IGF-1, erythrocyte sedimentation rate (ESR), adiponectin, leptin and estradiol
 - Other Serum Markers: IGF-1R, IRS-1, genomic and/or proteomic analysis
 - At week 5: a fasting insulin level will be evaluated.

- **Psycho-social evaluation:** Patients will have psycho-social evaluation using the FACT-B test and the PROMIS cancer fatigue short form at baseline, week 5, conclusion and 4 weeks after conclusion. (Forms detailed in CRFs in Appendix VII)
- **Outcomes:** Local recurrence, progression free survival, distant metastases and overall survival will be assessed through patient records after study has been completed.
- **Toxicity:** acute skin reaction or pain using the National Cancer Institute Common Toxicity Criteria (NCI CTC) version 4.0 scale²² will be assessed. Number of patients experiencing toxicity and time to occurrence of toxicity will be recorded (see Appendix III for toxicity scale). This toxicity will be compared to historical controls from TJUH who have also been treated for a 6-6.5 week course of radiation.

3.4 Primary Safety Endpoints

Acute toxicities will be evaluated by the CTCAE, Version 4.0. (<http://ctep.info.nih.gov>). If a patient has a serious adverse event such as all unexpected hospitalizations and all grade 4 and 5 SAEs, the patient will be removed from the trial. See Appendix III for scale.

4 Subject Selection and Withdrawal

Patients must have baseline evaluations performed prior to the first dose of study drug and must meet all inclusion and exclusion criteria. Results of all baseline evaluations will be reviewed by the Principal Investigator prior to enrollment, to verify that all inclusion and exclusion criteria have been satisfied. In addition, the patient must be thoroughly informed about all aspects of the study, including the study visit schedule and required evaluations and all regulatory requirements for informed consent. The written informed consent must be obtained from the patient prior to screening procedures being performed. The following criteria apply to all patients enrolled onto the study unless otherwise specified.

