4.5 Early Withdrawal of Subjects

4.5.1 When and How to Withdraw Subjects

Patients will be informed that they have the right to withdraw from the study at any time for any reason, without prejudice to their medical care. The investigator also has the right to withdraw patients from the study for any of the following reasons:

1. Intercurrent illness
2. Occurrence of an unacceptable adverse event such as a Grade ≥ 4 toxicity or $\geq 20\%$ weight
3. Missing more than 3 consecutive days of planned radiation
4. Patient request
5. Protocol violations based on the judgment of PI
6. Non-compliance
7. Administrative reasons
8. Failure to return for follow-up
9. General or specific changes in the patient's condition unacceptable for further treatment in the judgment of the investigator
10. Patients may withdraw from the study voluntarily at any time; however, the Principal Investigator reserves the right to remove patients from the study for any of the following reasons.
11. Radiation toxicity becomes too severe and the patient can no longer tolerate consecutive radiation treatments as determined by treating radiation oncologist.
12. Patients are hospitalized for another condition that is unrelated to breast cancer. Particularly admissions lasting longer than 4 days.
13. Patients develop any of the exclusionary conditions during treatments including: hepatic insufficiency, diabetes, disorders requiring corticosteroid treatment, renal failure or pregnancy.
14. Patients become sexually active and do not wish to use contraception or patients discontinue previous method of contraception and remain sexually active.

At the time of withdrawal, all study procedures outlined for the End of Study visit should be completed. The primary reason for a patient's withdrawal from the study is to be recorded in the source documents.

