4.5.2 Data Collection and Follow-up for Withdrawn Subjects

According to FDA regulations, when a subject withdraws from the study, the data collected on the subject to the point of withdrawal remains part of the study database and may not be removed.

A subject who is withdrawing needs to state whether he/she wishes to provide continued follow-up and further data collection subsequent to withdrawal from the interventional portion of the study.

If a subject withdraws from the interventional portion of the study, but agrees to continued follow-up of associated clinical outcome information as described in the previous bullet, the subject will continue follow up visit and evaluation per the protocol.

If a subject withdraws from the interventional portion of a study and does not consent to continued follow-up of associated clinical outcome information, study data related to the subject collected prior to the subject's withdrawal from the study will included in the study analysis. However, the subject's clinical data will not be used for dose escalation determination.

5 Study Drug/Therapy

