7.3 Subject Population(s) for Analysis

All subjects enrolled in the study who completed at least 4 food diaries per week during the diet modification phase will be used for analysis.

8 Safety and Adverse Events

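### Sections 3.4 and 4.5.1 give two removal rules for overlapping serious events, and the plan does not clearly say that a removed patient is followed up and counted in Aim 1b

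*Combined protocol and SAP*

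**What the plan says.** Section 3.4 (Primary Safety Endpoints) is written as an obligation. It gives as examples of a serious adverse event "all unexpected hospitalizations and all grade 4 and 5 SAEs, the patient will be removed from the trial".

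Section 4.5.1 (When and How to Withdraw Subjects) is written as a permission: "The investigator also has the right to withdraw patients from the study for any of the following reasons". Two items on its list overlap with 3.4. One is "Occurrence of an unacceptable adverse event such as a Grade ≥ 4 toxicity". The other is "Patients are hospitalized for another condition that is unrelated to breast cancer. Particularly admissions lasting longer than 4 days". The section also asks for the End of Study procedures to be done at withdrawal.

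Section 4.5.2 (Data Collection and Follow-up for Withdrawn Subjects) states that "the data collected on the subject to the point of withdrawal remains part of the study database and may not be removed". For a subject who leaves the interventional portion but agrees to further follow-up, "the subject will continue follow up visit and evaluation per the protocol". For one who leaves the interventional portion and declines, "study data related to the subject collected prior to the subject's withdrawal from the study will included in the study analysis".

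Section 7.3 (Subject Population(s) for Analysis) defines one population for everything: "All subjects enrolled in the study who completed at least 4 food diaries per week during the diet modification phase will be used for analysis".

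Section 7.2 tests Aim 1b as the proportion of patients with toxicity against a historical rate of about 80% with a 10-point margin, by exact binomial test at one-sided 0.05 with 90 patients.

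**The concern.** Take a patient with a two-day unexpected admission. Under 3.4 she must be removed from the trial. Under 4.5.1 her removal is a matter of judgement, and whether the hospitalisation item reaches her at all depends on the cause of the admission; the length of stay only adds emphasis. No text says which section prevails, so two similar patients could be handled differently.

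The statistical stake is in what follows removal. The study flowchart in 6.3 schedules acute toxicity assessment through radiation, to the end of the diet and at the follow-up visit. A patient removed early may miss part of that window. Two gaps make this matter for Aim 1b:

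- The follow-up option in 4.5.2 is tied to leaving the interventional portion, whereas 3.4 removes the patient from the trial. The withdrawal form in Appendix VII contains only statements made by the patient. Compulsory removal therefore has no clearly stated follow-up route.
- A patient removed partway through the diet cannot supply four diaries in every week of the planned diet phase. If 7.3 is read that way, she is not analysed at all, contrary to 4.5.2.

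If the patients lost by the second route tend to be those with toxicity, the observed rate falls and the test leans towards non-inferiority.

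**Working it through.** **Step 1. The removal rules side by side.**

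| Question | Section 3.4 | Section 4.5.1 |
|---|---|---|
| Is removal required? | Yes | No, it is the investigator's right |
| Severity trigger | Grade 4 and 5 SAEs | Grade 4 or higher toxicity, as an example of an unacceptable event |
| Hospitalisation trigger | Unexpected | Condition unrelated to breast cancer, particularly stays over 4 days |
| What the patient leaves | The trial | The study |

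The sections differ on obligation and on the hospitalisation trigger. The triggers overlap but are not identical. Grade 5 is death, so the practical conflict concerns grade 4 SAEs and hospitalisations.

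**Step 2. What happens to a removed patient's data.** Under 4.5.2 the data up to withdrawal stay in the database, and for a subject leaving the interventional portion they are analysed. Under 7.3, read strictly, the patient is outside the analysis set. The two sections give opposite answers for Aim 1b.

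**Step 3. Reproduce the plan's power.** Inputs from 7.2: n = 90, boundary 80% + 10% = 90%, assumed true rate 80%, one-sided alpha 0.05. The critical value c is the largest integer with P(X ≤ c | n, 0.90) ≤ 0.05.

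- P(X ≤ 75 | 90, 0.90) = 0.0333 and P(X ≤ 76 | 90, 0.90) = 0.0634, so c = 75.
- Power = P(X ≤ 75 | 90, 0.80) = 0.821, matching the stated 82%.

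**Step 4. Illustrate the strict reading of 7.3.** Assume that k patients, all with toxicity, are excluded from numerator and denominator. The test is then run on X − k out of 90 − k with its own critical value c′. Non-inferiority is declared when X ≤ c′ + k in the full 90, so the false non-inferiority rate is P(X ≤ c′ + k | 90, 0.90).

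| k excluded | n analysed | c′ | c′ + k | False non-inferiority rate |
|---|---|---|---|---|
| 0 | 90 | 75 | 75 | 3.3% |
| 1 | 89 | 74 | 75 | 3.3% |
| 3 | 87 | 72 | 75 | 3.3% |
| 4 | 86 | 72 | 76 | 6.3% |
| 9 | 81 | 67 | 76 | 6.3% |
| 10 | 80 | 66 | 76 | 6.3% |

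The rate is flat at 3.3% for k = 1 to 3 and at 6.3% for k = 4 to 10, because the critical value moves in whole patients.

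**Step 5. The other reading.** If 4.5.2 governs and follow-up is complete, all 90 patients are analysed, the threshold stays at 75 and the rate stays at 3.3%.

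**The case against.** A reader might infer that removal ends toxicity follow-up, so that the worst outcomes leave the data. The documents do not support that. Section 4.5.2 comes directly after the withdrawal list. It keeps everything recorded up to withdrawal and provides for continued visits by agreement. Section 4.5.1 requires End of Study procedures at withdrawal, and 8.1.6 requires unresolved adverse events to be followed. Leaving the trial is not leaving the database, and a patient whose skin toxicity is already recorded still counts under 4.5.2.

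It can also be said that the arithmetic above is not caused by 3.4 or 4.5.1. That is right: whole-patient loss arises only through 7.3. Three further limits stand. The documents give no removal rate. The 3.4 triggers are not confined to skin events, so assuming that every excluded patient had toxicity is an extreme case. And part of the step from 3.3% to 6.3% is discreteness: with n = 86 and no selective exclusion, the exact test already has size 4.6%.

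The objection does not remove the conflict between obligation and permission, or the different hospitalisation triggers. It also does not show that 4.5.2 covers a patient removed by rule, or that 4.5.2 overrides 7.3.

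**Conclusion.** The contradiction between 3.4 and 4.5.1 is established from the text and needs no assumption. That 4.5.2 does not clearly extend to compulsory removal is a gap in wording; the section is not missing, and it answers much of the worry about lost data.

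The effect on Aim 1b is conditional. It requires the strict reading of 7.3, and it requires the excluded patients to be mainly those with toxicity. On those assumptions, and at a true rate of 90%, up to 3 exclusions among 90 change nothing, while 4 to 10 raise the false non-inferiority rate from 3.3% to 6.3%, above the nominal 5%. These figures illustrate a mechanism and do not predict what will happen. If 4.5.2 is followed with complete follow-up, the stated error rate holds.

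The point is worth correcting because it concerns serious events, the possible bias favours the hypothesis under test, and the remedy is cheap. Nothing here bears on which removal rule is clinically right.

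**What to change.** 1. Reconcile 3.4 and 4.5.1 into a single rule that says whether removal is required or discretionary and which hospitalisations count. The clinical content is the sponsor's decision.
2. State in that rule that the follow-up in 4.5.2 applies to patients removed by the investigator or by protocol: with consent, toxicity assessment continues to the visit 4 weeks after the diet.
3. State in 7.2 or 7.3 that removed patients are counted in Aim 1b regardless of the four-diary rule.

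The cost is a protocol amendment to wording. The withdrawal form already offers continued follow-up after stopping study treatment, so it needs at most an added line for removal not initiated by the patient. Sample size and test are unchanged.

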4.1 Inclusion Criteria

1. Pathologically proven diagnosis of DCIS or invasive breast cancer
2. Ability to have breast conservation as determined by the judgment of the radiation oncologist, for which the radiation oncologist has determined that he or she will only treat the whole breast and not regional lymph nodes
3. The patient must be female
4. Age ≥ 18
5. If multifocal breast cancer, then it must be able to be resected through a single lumpectomy incision
6. Appropriate stage for protocol entry, including no clinical evidence for distant metastases, based upon the following minimum diagnostic workup:
 - History/physical examination, including breast exam and documentation of weight and Karnofsky Performance Status of 80-100% at study entry.
7. Women of childbearing potential must be non-pregnant and non-lactating and willing to use medically acceptable form of contraception during radiation therapy
8. Patient must be capable of and provide study specific informed consent prior to study entry
9. BMI ≥ 21

10. Weight ≥ 100 lbs
11. No prior history of non-breast invasive malignancies in the past 1 years
12. Patient must not have any of the following severe, active co-morbidity, defined as follows:
 - Unstable angina and/or congestive heart failure requiring hospitalization within the last 6 months
 - Transmural myocardial infarction within the last 6 months
 - Acute bacterial or fungal infection requiring intravenous antibiotics at the time of registration;
 - Chronic Obstructive Pulmonary Disease exacerbation or other respiratory illness requiring hospitalization or precluding study therapy within 30 days before registration;
 - Hepatic insufficiency resulting in clinical jaundice and/or coagulation defects; note, however, that laboratory tests for liver function and coagulation parameters are not required for entry into this protocol
 - Acquired Immune Deficiency Syndrome (AIDS) or HIV positive based upon current CDC definition; note, however, that HIV testing is not required for entry into this protocol. The need to exclude patients with AIDS or HIV from this protocol is necessary because anti-retrivirals may alter patient metabolism.
 - Gastrointestinal/Malabsorption disorder at the discretion of the Principal Investigator
 - Inflammatory Bowel Disease
 - Celiac Disease
 - Chronic Pancreatitis
 - Chronic Diarrhea or Vomiting
 - Active Eating Disorder
 -
13. Patient must not have active systemic lupus erythematosus, or any history of active scleroderma, or dermatomyositis with active rash
14. No prior radiotherapy to the ipsilateral breast or prior radiation to the region of the breast that would result in overlap of radiation therapy fields
15. Not currently taking steroids
16. No history of or current active drug/alcohol dependence.
17. No patients being decisionally impaired.

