6.2 Study Visit Schedule

6.2.1 Screening

Eligibility of patients will be verified based on clinical staging and any need for adjuvant chemotherapy as well as previously stated eligibility criteria. Those eligible patients will receive detailed information about the study including a step-by-step outline of proposed treatment including radiation therapy and diet modification. Patients will be informed of possible risks and benefits. Informed consent will be obtained from patients. A full history and physical examination will be performed on consented patients. Baseline weight and BMI will be taken. In addition, blood will be drawn for eligibility measurements of beta-hCG if appropriate.

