6.2.2 Phase I—Pre-treatment

Visit 1: Patients will report to the Radiation Oncology Department for radiation treatment planning to include CT simulation. Food diaries from the previous 7-10 days will be collected and analyzed to create a diet plan for each patient. Integrative medicine will meet with patients to counsel them on lifestyle changes and behavioral aspects of dietary modification. Dietary counselors will give patients guidelines for dietary modification including the appropriate amount of calories that each patient should be receiving and what kinds of foods they should avoid or eat more of. Nutritional counseling will be done using behavioral cues to encourage adherence (see Appendix V for worksheets). Patients will be instructed to begin their new diet starting at this visit and to continue logging foods into their journals. They will complete the journal daily. Patients will undergo a focused examination to assess initial breast appearance and texture for comparison as patients receive radiation therapy. Fasting blood will be drawn for baseline laboratories at this visit. Clinical measurements will include CBC w/diff, CMP, HbA1c, IGF-1, adiponectin, leptin, estradiol, triglycerides, insulin, ESR. Separately, blood samples will also be

analyzed for the following: IGF-1R, IRS-1 and other experimental endpoints such as genomic or proteomic alterations. Baseline psychosocial evaluation will be done using the FACT-B form as well as a baseline fatigue assessment using the PROMIS cancer fatigue short form (see appendix XI). Weight, height, vital signs, bioimpedance and caliper measurements will be done.

Phone Intervention: Patients will be contacted at least once a week during the time they are keeping the food journal to determine if help is needed.

Visit 2: Week 1 or day 7 (± 2 day) of diet. Weight will be measured and vital signs will be taken. Food diary from previous week to be collected, as well as 24hr recall of diet.

Visit 3: Week 2 of diet. Weight will be measured and vital signs will be taken. Food diary from previous week to be collected, as well as 24hr recall of diet.

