 - Chronic Diarrhea or Vomiting
 - Active Eating Disorder
- Currently using steroids
-
- Active/history of substance abuse or dependency to include prescription or illicit drugs as well as alcohol.
- Decisionally impaired patients.

Checklist for Screening Visit:

Informed Consent for Trial Obtained	
All Sections of CRF Completed	
Inclusion/Exclusion Criteria Evaluated	
Blood draw: Beta-HCG	
H&P; Performance Status	
Weight, BMI	
Based on screening patient appears eligible	

CAREFOR Study Case Report Form (CRF)—Radiation Treatment Planning Visit

Date of Sim Visit: _____

Lumpectomy Details

Please indicate the actual date of the lumpectomy, whether or not there were any post-op complications and the status of the Path report:

Surgery DatePre-op DiagnosisPost-Op Complications_____

Path Report Received? Y or N

Attach a copy of the Path Report to this visit.

Verify Allergies:_____

_____**Changes to Current Medications (indicate dose, route, frequency and start date):**

Medication

Dose

Route

Frequency

Start Date

Physical Examination

Height: _____ Weight: _____ BMI: _____
 Vital Signs: BP: _____ HR: _____ Temp: _____ RR: _____
 Caliper Measurements: _____

Bioimpedance Measurement: _____

Please indicate the status (normal or abnormal) of each system listed below. If abnormal, please make notes. Give detailed description of breast exam in the notes section.

Organ System	Status	Notes
CVS	Normal Abnormal	_____
Pulm	Normal Abnormal	_____ _____
GI	Normal Abnormal	_____ _____
Neuro	Normal Abnormal	_____ _____
Breast	Normal Abnormal	_____ _____ _____

CTCAE v4.0 Evaluation

Please evaluate the patient at baseline for comparison during and post-radiation.

Adverse Event	Grade				
	1	2	3	4	5
Dermatitis radiation	Faint erythema or dry desquamation	Moderate to brisk erythema; patchy moist desquamation, mostly confined to skin folds and creases; moderate edema	Moist desquamation in areas other than skin folds and creases; bleeding induced by minor trauma or abrasion	Life-threatening consequences; skin necrosis or ulceration of full thickness dermis; spontaneous bleeding from involved site; skin graft indicated	Death
Definition: A finding of cutaneous inflammatory reaction occurring as a result of exposure to biologically effective levels of ionizing radiation.					
Skin hyperpigmentation	Hyperpigmentation covering <10% BSA; no psychosocial impact	Hyperpigmentation covering >10% BSA; associated psychosocial impact	-	-	-

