Abbreviations: PROMIS, Patient-Reported Outcomes Measurement Information System; FATEXP, Fatigue Experience; FATIMP, Fatigue Impact.
Reprinted with permission of the PROMIS Health Organization and the PROMIS Cooperative Group.

Checklist for Sim Visit:

Pathology Report Obtained and Attached	
Baseline Labs: CBC w/diff, CMP, HbA1c Serum: IGF-1, adiponectin, leptin, estradiol, triglycerides, ESR, insulin, glucose	
Blood Sample sent to [name] lab for further analysis	
All Sections of CRF Completed	
FACT-B Completed by patient	
Weight, BMI, Body fat percent, bioimpedance	
Food diaries collected at this visit	
Dietary Counseling for caloric restriction diet alterations	

Please attach a copy of patient's labs when available.
Please attach a copy of food diary.

CAREFOR Study Case Report Form (CRF)—Diet Support Visit: Day 7 of CR Diet

Date of Visit: _____

Changes to Current Medications (indicate dose, route, frequency and start date):

Medication	Dose	Route	Frequency	Start Date
_____	_____	_____	_____	_____
_____	_____	_____	_____	_____
_____	_____	_____	_____	_____

Height: _____ Weight: _____ BMI: _____
 Vital Signs: BP: _____ HR: _____ Temp: _____ RR: _____

Food Diary Received and Completed: Y or N
 If no, must collect at next visit.

CAREFOR Study Case Report Form (CRF)—Diet Support Visit: Day 14 of CR Diet

Date of Visit: _____

Changes to Current Medications (indicate dose, route, frequency and start date):

Medication	Dose	Route	Frequency	Start Date
_____	_____	_____	_____	_____
_____	_____	_____	_____	_____
_____	_____	_____	_____	_____

Height: _____ Weight: _____ BMI: _____
 Vital Signs: BP: _____ HR: _____ Temp: _____ RR: _____

Food Diary Received and Completed: Y or N
 If no, must collect at next visit.

CAREFOR Study Case Report Form (CRF)—Radiation Treatment

Date of Visit: _____ Weeks of Radiation Completed: _____

Changes to Current Medications (indicate dose, route, frequency and start date):

Medication	Dose	Route	Frequency	Start Date

Food Diary Received and Completed: Y or N If no, must collect at next visit.

Physical Examination

Height: _____ Weight: _____ BMI: _____
 Vital Signs: BP: _____ HR: _____ Temp: _____ RR: _____

Please indicate the status (normal or abnormal) of each system listed below. If abnormal, please make notes. Give detailed description of breast exam in the notes section.

Breast	Normal	Abnormal	_____
Erythema	Mild	Moderate	Severe
Hyperpigmentation	Mild	Moderate	Severe
Desquamation	Yes	No	
Dermatitis	Yes	No	

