Appendix X.

Thomas Jefferson University Kimmel Cancer Center

CAREFOR Inclusion/Exclusion Criteria Checklist

Inclusion Criteria:

Patients must meet all of the following criteria in order to be considered for entry into the CAREFOR trial.

- Pathologically proven diagnosis of DCIS or invasive breast cancer*
- Ability to have breast conservation as determined by the judgment of the radiation oncologist*
- The patient must be female*
- Age ≥ 18*
- If multifocal breast cancer, then it must be able to be resected through a single lumpectomy incision*
- Appropriate stage for protocol entry, including no clinical evidence for distant metastases, based upon the following minimum diagnostic workup:*
- History/physical examination, including breast exam and documentation of weight and Karnofsky Performance Status of 80-100% at study entry.*
- Women of childbearing potential must have a negative serum pregnancy test within 14 days of study entry*
- Women of childbearing potential must be non-pregnant and non-lactating and willing to use medically acceptable form of contraception during radiation therapy*
- Patient must capable of and provide study specific informed consent prior to study entry*
- BMI ≥ 21*
- Weight ≥ 100 lbs*
- No prior history of non-breast invasive malignancies in the past 1year*
- Patient must not have any of the following severe, active co-morbidity, defined as follows:*
 - Unstable angina and/or congestive heart failure requiring hospitalization within the last 6 months*
 - Transmural myocardial infarction within the last 6 months*
 - Acute bacterial or fungal infection requiring intravenous antibiotics at the time of registration;*
 - Chronic Obstructive Pulmonary Disease exacerbation or other respiratory illness requiring hospitalization or precluding study therapy within 30 days before registration;*

- *Hepatic insufficiency resulting in clinical jaundice and/or coagulation defects; note, however, that laboratory tests for liver function and coagulation parameters are not required for entry into this protocol*
- *Acquired Immune Deficiency Syndrome (AIDS) or HIV positive based upon current CDC definition; note, however, that HIV testing is not required for entry into this protocol. The need to exclude patients with AIDS or HIV from this protocol is necessary because anti-retrivirals may alter patient metabolism.*

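### Inclusion item 7 and Appendix X require contraception only during radiation therapy, although the planning CT and at least 14 days of diet separate the only hCG test scheduled in the available text from the first fraction

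*Combined protocol and SAP*

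**What the plan says.** **The criterion.** Section 4.1 item 7 requires women of childbearing potential to be "willing to use medically acceptable form of contraception during radiation therapy"; Appendix X carries the same requirement, "non-pregnant and non-lactating and willing to use medically acceptable form of contraception during radiation therapy". The opening of section 4 makes the criteria general: "The following criteria apply to all patients enrolled onto the study unless otherwise specified". Section 4.2 item 8 excludes a woman with a positive serum hCG.

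**The test.** Under section 6.2.1, "blood will be drawn for eligibility measurements of beta-hCG if appropriate". The Appendix VII checklist for the screening visit has the matching line, "Blood draw: Beta-HCG". Appendix X adds that the negative serum test must fall no more than 14 days from study entry, but does not tie entry to a visit.

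**What follows the test.** Visit 1 (section 6.2.2) is for "radiation treatment planning to include CT simulation", and "Patients will be instructed to begin their new diet starting at this visit". Section 5.1 sets at least two weeks of diet before radiation. The laboratory line on the simulation-visit checklist in Appendix VII reads "Baseline Labs: CBC w/diff, CMP, HbA1c Serum: IGF-1, adiponectin, leptin, estradiol, triglycerides, ESR, insulin, glucose"; hCG is not in it, nor among the Visit 1 labs in section 6.2.2.

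**Other text on contraception.**
- The screening CRF in Appendix VII asks a sexually active woman which method she uses and, if none, whether she would use one throughout the study or treatment period.
- The Appendix VII eligibility checklist requires willingness to use contraception (or not being sexually active, or being post-menopausal) and states no period.
- Section 4.5.1 items 13 and 14 let the investigator withdraw a woman who becomes pregnant, who becomes sexually active and declines contraception, or who stops her method while still sexually active.

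**The concern.** The criterion names a period, and the period starts with radiation. The pregnancy test comes earlier. Between the two lie the planning CT and the first weeks of the diet.

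Take a sexually active woman who uses no contraception at entry and is willing to start only when radiation starts. She satisfies item 7 and Appendix X as written. If she conceives after the screening test, no scheduled test in the available text would show it before the planning CT or before the 60-66 Gy course (section 6.4.1). A protocol that excludes women with a positive hCG presumably does not intend that.

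There is also a risk of uneven application. Staff working from the screening CRF would probably not enrol this woman; staff working from item 7 could.

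**Working it through.** **1. The plan's own timeline.** The Study Summary gives at least 2 weeks of diet before radiation, 6 to 6.5 weeks during it and at least 2 weeks after:
- 2 + 6 + 2 = 10 weeks
- 2 + 6.5 + 2 = 10.5 weeks

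Both agree with the stated total of at least 10 weeks, so the two-week lead-in is a firm part of the schedule.

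**2. The floor.** The hCG test is an eligibility measurement at screening, so it does not follow simulation. The diet starts at simulation (section 6.2.2) and lasts at least 2 weeks before radiation (section 5.1).

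Interval outside item 7 ≥ 2 × 7 = 14 days.

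This needs no assumption about the food diary.

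**3. With the diary after the draw (assumption).** Interval = diary days + 14.

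| Baseline diary | Source | Interval |
|---|---|---|
| 7 days | section 5.1 | 7 + 14 = 21 days |
| 10 days | section 5.1 | 10 + 14 = 24 days |
| 14 days | section 5.2.1 | 14 + 14 = 28 days |

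The table in section 6.1 (normal diet in weeks 1-2, restricted diet in weeks 3-4, radiation from week 5) also gives (5 − 1) × 7 = 28 days from the start of week 1. Section 11 puts consent before any study procedure, so a study diary follows consent. That makes this order plausible, but the documents do not state whether the blood draw or the diary comes first.

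**4. What does not fix the interval.** Appendix X's 14-day window is measured from study entry, which is not placed on the schedule. If entry were the first diary day and the test 14 days earlier, the interval would be 21 + 14 = 35 to 28 + 14 = 42 days; other readings shorten it. The section 6.3 flowchart also places surgery between screening and simulation with no stated gap. So 14 days is a secure minimum, and 28 days is not a maximum.

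**5. The contraception texts side by side.**

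| Place | Period stated | Force |
|---|---|---|
| 4.1 item 7, Appendix X | Radiation only | Entry criterion |
| Screening CRF, Appendix VII | Whole study or treatment period | Data question for women using no method; no stated consequence of a negative answer |
| Eligibility checklist, Appendix VII | None | Entry checklist |
| 4.5.1 items 13-14 | None for stopping or declining contraception; during treatment for pregnancy | Investigator's discretion, after enrolment |

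The only text with an explicit period covering the weeks before radiation is the CRF question, and it is not a criterion.

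**The case against.** The strongest reply is that the woman described above is already dealt with. The screening CRF asks about exactly her situation, the screening checklist requires every CRF section to be completed, and the Appendix VII checklist demands willingness without a time limit. Enrolling her would mean disregarding her CRF answer. This stands as a description of likely practice and makes the practical gap much smaller than item 7 alone suggests. It does not make contraception before radiation an explicit entry requirement.

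Four stronger readings are tempting and should not be drawn:
- **That contraception is the only planned protection before radiation.** Item 7 also requires that the woman not be pregnant, pregnancy is a withdrawal reason, patients are contacted weekly while keeping the journal, and they are questioned and examined at on-treatment visits. None of these is a pregnancy test, but they are safeguards.
- **That the flowchart proves there is no retest.** It has no hCG row, but it also omits the screening hCG that section 6.2.1 schedules, so its silence shows little. The evidence is the lab lists in section 6.2.2 and Appendix VII. Appendix IV, the visit schedule, has no body in the available text and could not be checked.
- **That two independent places confirm the wording.** Appendix X differs from section 4.2 elsewhere (2 years disease-free against 1 year), so it may be an unsynchronised copy.
- **That the length of the interval measures risk.** It does not; nothing in the documents gives the number of women affected.

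It is also fair to say that the consent form, which was not available, may state a longer period, and that rewording adds no test and would not detect a very early conception missed at screening.

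**Conclusion.** The point holds as a minor patient-safety improvement. Item 7 states a contraception period that begins too late, by at least 14 days relative to the screening test, and by 21 to 28 days if the diary follows the draw. The planning CT falls in that interval. The criterion is narrower than the question the trial itself asks on its screening CRF.

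A reader might infer that the protocol leaves women unprotected before radiation. The documents do not support that: the CRF question, the untimed checklist item and discretionary withdrawal cover much of the interval in practice. What remains is a mismatch in which the binding text is the weakest one.

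The conclusion rests on the visit and lab lists in the available text being complete as to hCG testing, and on the consent form not already resolving the matter. Sample size, power and alpha are untouched.

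**What to change.** 1. In section 4.1 item 7 and Appendix X, replace the reference to radiation therapy as the contraception period with: *from the screening serum beta-hCG test through the end of the study treatment period (at minimum the last radiation fraction)*. The sponsor should state whether study treatment ends with the last fraction or with the diet.
2. Leave the screening CRF question as broad as it is. Item 7 should be widened to meet it, not the reverse.
3. Add the same period to the contraception line of the Appendix VII eligibility checklist.
4. Check that the consent form states the same period.

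The cost is an IRB amendment to a few lines of text and a consent-form check, with no new visit or procedure. Some women would start contraception about 2 to 4 weeks earlier (14 to 28 days). A repeat hCG before simulation or the first fraction would be a separate decision and is not needed for this correction.
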